8.3.5 ADVERSE EVENT REPORTING

In consultation with the Principal Investigator (PI) and the study clinician, a trained member of the study team will be responsible for conducting an evaluation of an AE and shall report the results of such evaluation to the reviewing IRB either at the time of continuing review or within 10 working days of becoming aware of the event if the event is considered to be serious or meets the definition of an unanticipated problem involving risks to study subjects or others.

8.3.6 SERIOUS ADVERSE EVENT REPORTING

In consultation with the PI and the study clinician, a trained member of the study team will be responsible for conducting an evaluation of a SAE and shall report the results of such evaluation to the reviewing IRB as soon as possible, but in no event later than 10 working days after the investigator first learns of the event.

8.3.7 REPORTING EVENTS TO PARTICIPANTS

Following IRB review of any AEs or SAEs, the PI will follow the IRB's recommended actions. This may include, but is not limited to, modifying the informed consent document or process, re-consenting current participants, providing information to past or current participants (e.g. whenever the information may relate to the participant's willingness to continue participants), and modifications to the protocol/research plan.

8.3.8 EVENTS OF SPECIAL INTEREST

N/A

8.3.9 REPORTING OF PREGNANCY

Women who are currently pregnant, lactating, or planning to become pregnant during the study are excluded from this study. This is due to the hormonal changes that may alter headache patterns. If any participant who is still undergoing acupuncture treatment expectedly or unexpectedly becomes pregnant while active in the trial, the participant will be withdrawn from the study by the Principal Investigator. The participant will be asked to complete an early withdrawal phone call in 7-14 days from the date the intervention was discontinued for safety follow-up.

If any participant who has completed all acupuncture treatment sessions expectedly or unexpectedly becomes pregnant, the participant may remain in the study until study completion.

8.4 UNANTICIPATED PROBLEMS

8.4.1 DEFINITION OF UNANTICIPATED PROBLEMS

This protocol uses the definition of Unanticipated Problems as defined by the Office for Human Research Protections (OHRP). OHRP considers unanticipated problems involving risks to participants or others to include, in general, any incident, experience, or outcome that meets all of the following criteria:

1. Unexpected in terms of nature, severity, or frequency given (a) the research procedures that are described in the protocol-related documents, such as the IRB-approved research protocol and informed consent document; and (b) the characteristics of the participant population being studied;
2. Related or possibly related to participation in the research ("possibly related" means there is a reasonable possibility that the incident, experience, or outcome may have been caused by the procedures involved in the research); and
3. Suggests that the research places participants or others at a greater risk of harm (including physical, psychological, economic, or social harm) than was previously known or recognized.

8.4.2 UNANTICIPATED PROBLEMS REPORTING

The PI will report unanticipated problems (UPs) to the reviewing IRB. The UP report will include the following information:

- Protocol identifying information: protocol title and number, PI's name, and the IRB project number
- A detailed description of the event, incident, experience, or outcome
- An explanation of the basis for determining that the event, incident, experience, or outcome represents an UP
- A description of any changes to the protocol or other corrective actions that have been taken or are proposed in response to the UP

To satisfy the requirement for prompt reporting, UPs will be reported using the following timeline:

- UPs will be reported to the IRB as soon as possible, but no later than 10 working days after the investigator first learns of the event

8.4.3 REPORTING UNANTICIPATED PROBLEMS TO PARTICIPANTS

Following IRB review of any unanticipated problems, the PI will follow the IRB's recommended actions. This may include, but is not limited to, modifying the informed consent document or process, re-consenting current participants, providing information to past or current participants (e.g. whenever the information may relate to the participant's willingness to continue participants), and modifications to the protocol/research plan.

9 STATISTICAL CONSIDERATIONS

9.1 STATISTICAL HYPOTHESES

- **Primary:**
We hypothesize that quality of life, as assessed by MG-QOL15, will improve with acupuncture treatment compared to no acupuncture treatment.
- **Secondary:**
We hypothesize that quality of life, as assessed by MG ADL, will improve with acupuncture treatment compared to no acupuncture treatment.

9.2 SAMPLE SIZE DETERMINATION

We anticipate enrolling 10 subjects in each study group. The primary analysis is a two-sided two sample t-test comparing the mean change in MG-QOL15 over 12-weeks weeks from a delayed start 2-group design. We hypothesize that Group 1 who received acupuncture treatment will experience a change in QOL over the 12-weeks while Group 2, the untreated control, will not. We will analyze the data such that the opposite could be shown. The null hypothesis is that there will be no difference between treatment

groups. Our sample size of 10 subjects in each group achieves 80% power at a 5% significance level to detect a 1.32 SD difference in mean change in MG-QOL15 between groups (PASS software version 11). No interim analyses are planned. The potential effect on our power if for a range of true effect sizes are displayed in the table below. If our final analysis shows a smaller effect size than 1.32 SD difference, we will include and post-hoc power analysis with the results.

N	δ/σ	Power	Alpha
20	0.9	0.44	0.05
20	1.0	0.56	0.05
20	1.3	0.78	0.05
20	1.6	0.91	0.05

N = total sample size, 1:1 Randomization to 2 groups;

δ = treatment effect (change);

σ = standard deviation.

Based on preliminary estimates, we do not anticipate difficulty recruiting 20 subjects. HealthPartners clinicians see approximately 4 individuals with MG per month at the Neuroscience Center and Park Nicollet Clinics, approximately 50 annually. Therefore, we will need a 40% enrollment rate to reach our recruitment goal in the allotted time frame. In addition, we also plan to recruit and enroll from other HealthPartners clinics and within the community. If we see a 20% reduction in sample size due to dropout, withdrawal, or missing data, our power will be 71% to detect a similar effect size. This, and other possible changes in power due to attrition, are listed in the table below. *Note: The original sample size estimation was for 20 individuals; however, we wrote the protocol so that we could replace anyone who did not start the intervention. Thus, we are increasing the enrollment target to 25, which is not reflected in the original power analysis.

N	δ	σ	Power	Alpha
16	9.5	7	0.71	0.05
18	9.5	7	0.77	0.05
20	9.5	7	0.82	0.05

N = total sample size; δ = treatment effect (change); σ = standard deviation.

9.3 POPULATIONS FOR ANALYSES

All analyses will be performed on an intention-to-treat basis. If poor attendance at acupuncture treatments is observed, we will perform a per-protocol analysis as a sensitivity analysis.

9.4 STATISTICAL ANALYSES

9.4.1 GENERAL APPROACH

Discrete variables will be summarized using frequencies and percentages, while continuous variables will be summarized by means and standard deviations. If the continuous variables are found to be skewed,

we will instead report medians and interquartile ranges. Statistical significance will be determined using p-values less than 0.05 and 95% confidence intervals, unless otherwise indicated. All inferential tests will be two-sided. For descriptive statistics (means, SDs, proportions) where no inferential statistics were conducted, we will refrain from making confirmative statements. All covariates will be pre-specified in the sections below. Any additional analyses will be described as post-hoc and exploratory.

Distribution of the outcome variables will be assessed prior to conduct of our analyses to determine if the planned tests are appropriate. If variables are found to be non-normally distributed we will explore the use of log-transformations or non-parametric tests such as the Wilcoxon-Rank Tests.

9.4.2 ANALYSIS OF THE PRIMARY ENDPOINT(S)

The MG-QOL15 scores will be collected for each participant at several time points. The primary outcome, change in MG-QOL15 scores over the first 12-weeks, will be calculated using the first and second collected scores for both groups. Group 1 will have received the full acupuncture intervention between the two measurements while Group 2 will act as the untreated control. We will present the mean change by group with corresponding standard deviations. Analysis of covariances (ANCOVA) with adjustment for baseline MG-QOL15 and covariates identified above will be used to determine if a significant ($p<0.05$) intervention effect is present. If the model identifies a significant difference in change of MG-QOL15 associated with acupuncture treatment, next steps will assess if this change is still present 12-weeks after completing the full acupuncture treatment. Using data from Group 1, a paired t-test will be used to compare the MG-QOL15 scores directly after treatment (Post-treatment Assessment 1) and scores 12-weeks post-treatment (Post-treatment Assessment 2). (Refer to Schema on page 4 for data collection points.)

Prior to analysis, we will plot our outcomes to examine their distribution and decide whether we should consider non-parametric analyses. Only subjects with complete data from both pre-treatment assessment and 12-week assessment will be included in the final analysis. Data will be analyzed per an intent-to-treat approach regardless of actual treatment received. If a large proportion of missing data is noted, we will compare baseline characteristics of subjects who completed the treatment with those who were lost to follow-up.

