1.2 SCHEMA

1.3 SCHEDULE OF ACTIVITIES

	Pre-screening	Pre-treatment 1	Pre-treatment 2	Study Intervention	Post-treatment 1	Post-treatment 2	2-week follow up call
Group 1: Immediate Start	Visit 0	Visit 1	N/A	Visit 2-25	Visit 26	Visit 27	N/A
Group 2: Delayed Start		Visit 1	Visit 2	Visit 3-26	Visit 27	N/A	Visit 28
Review Eligibility	X						
Informed Consent		X					
Randomization		X					
Demographics		X					
Medication Review		X	X	X	X	X	
Symptom Severity Scale (Treatment Log)				X	X	X	X
MG-QOL15		X	X		X	X	
MG-ADL		X	X		X	X	
Adverse Events (AE) Reporting				X	X	X	X
Treatment Adherence				X			

VISIT SCHEDULE DESCRIPTION

All in-person visits will take place at: **HealthPartners Neuroscience Center, [name], HealthPartners Clinic St. Paul Como, [name], or Healing Response Acupuncture & Functional Neurology, [name].**

1. Pre-screening Phone Call (Groups 1 & 2)

- Duration: Approximately 30 minutes
- Research staff will:
 - Provide potential participants information about the study and ask whether they are interested in participating.
 - Determine whether they meet the inclusion/exclusion criteria for the study.
 - Ask participants for permission to communicate through e-mail for the study
 - Assist participants with setting up an e-mail account, if they do not have one.

- Schedule Pre-treatment Visit if the person is eligible for the study and e-mail the person the Informed Consent, Health Insurance Portability and Accountability Act (HIPPA), and HealthPartners non-discrimination forms.

2. Pre-treatment Visit 1 (Groups 1 & 2)

- Duration: Approximately 1 hour via phone
- Research staff will:
 - Review the Informed Consent and HIPPA documents with potential participants.
 - Answer any questions of potential participants and ensure they understand the expectations of the study.
 - Ask participants to electronically sign the Informed Consent and HIPAA documents via Research Electronic Data Capture (REDCap), a secure web-based system, and provide them electronic copies for their records.
 - Complete the Demographics and Medication Review short forms in the relevant electronic case report forms (eCRFs) in REDCap.
 - Interview patients using the Myasthenia Gravis Quality of Life Scale (MG-QOL15) and Activities of Daily Living (MG ADL) surveys and document in REDCap.

3. Pre-treatment Visit 2 (Group 2 only)

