6.1.2 ADMINISTRATION AND/OR DOSING

Acupuncture Treatment Methods:

Group 1 will receive twice-weekly acupuncture immediately over 12-weeks. After a 12-week delay, Group 2 will also receive twice-weekly acupuncture over 12-weeks. Acupuncture treatments will be separated by a minimum of 2 days and a maximum of 14 days, unless a participant has an illness, such as COVID-19. In this case, additional time may be allowed, as determined by the investigator. Treatment methods will be identical for both groups and are described below.

Standard, sterile stainless-steel, disposable needles (DongBang™ Corporation, Spring Ten 0.22 x 30mm; Boryeoung, Republic of Korea) will be inserted in the acupuncture point locations (described below), with approximately 23-32 needles used for each treatment session. The number of needles used will be based

on the patient-reported symptoms. The depth of the needle insertion will be approximately 10-20mm, depending on the region of the body undergoing treatment. Needle reaction (soreness, numbness or distended feeling around the point, also known as a Deqi sensation) will occur during the initial insertion. Following 10 minutes of retention, some of the needles will be rotated in order to maintain Deqi sensation. Maintaining Deqi sensation has been shown to increase the effectiveness of acupuncture.^{10,11} All needles will be left in place for a total of 30 minutes, which is a typical duration in acupuncture practice.

Acupuncture points were selected for their classical Traditional Chinese Medicine indications relevant to MG symptom pathology, as well as their modern biomedical muscular, immunological, and neurological actions. The anatomical location for each point will be based on the World Health Organization's acupuncture point guideline.¹² Traditional Chinese manual acupuncture will be used at up to 32 acupuncture points. During treatment, acupuncture needles can be removed due to extreme pain or discomfort, so as not to exceed the removal of more than 4 needles.

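### The durability step in section 9.4.2 tests movement after treatment ends, not whether the MG-QOL15 improvement over baseline remains

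*Combined protocol and SAP*

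**What the plan says.** Section 9.4.2 defines the primary outcome as the MG-QOL15 change between the first and second collected scores. For Group 1 that is baseline to Post-treatment 1.

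A follow-on step is conditional on the primary result: "If the model identifies a significant difference in change of MG-QOL15 associated with acupuncture treatment", then "next steps will assess if this change is still present 12-weeks after completing the full acupuncture treatment". One method is given for it, using Group 1 alone: "a paired t-test will be used to compare the MG-QOL15 scores directly after treatment (Post-treatment Assessment 1) and scores 12-weeks post-treatment".

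Section 9.4.1 sets the general convention: "Statistical significance will be determined using p-values less than 0.05 and 95% confidence intervals, unless otherwise indicated". All tests are two-sided. The same section adds: "Any additional analyses will be described as post-hoc and exploratory".

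The scores needed for a baseline comparison are already scheduled. At Pre-treatment Visit 1 staff will "Interview patients using the Myasthenia Gravis Quality of Life Scale (MG-QOL15) and Activities of Daily Living (MG ADL) surveys and document in REDCap", and section 1.3 repeats MG-QOL15 at Post-treatment Visit 2, which only Group 1 has. Group 2 offers no untreated comparison at that point, because section 6.1.2 states: "After a 12-week delay, Group 2 will also receive twice-weekly acupuncture over 12-weeks".

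**The concern.** The stated question and the named test have different null hypotheses. The question is whether a gain measured from baseline survives to week 24. The test asks whether the mean moved between weeks 12 and 24.

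The two can disagree in either direction. A non-significant paired result could be reported as a lasting effect when about half the benefit has gone. A significant one could be reported as benefit lost when a good part remains. Because the test is two-sided, a significant result could even reflect further improvement.

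Nothing elsewhere fills the gap. Section 9.4.3 concerns MG ADL, and the mixed models in section 9.4.9 are for exploratory outcomes such as medication changes and adherence. No retention margin or reading rule for the paired test is given. If the baseline comparison is not written in now, section 9.4.1 means it can be added later only as a post-hoc analysis.

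**Working it through.** **Inputs.** From section 9.2: 10 per group, planned effect 9.5 points, SD 7. From section 9.4.1: two-sided 0.05. The SD of the Post-treatment 1 to 2 difference is not in the documents. I assume the plan's 7 and show 5 to 9. I also show n = 8 (the plan's 20% attrition case) and n = 12 (about half of the enrolment target of 25).

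**The plan's own figure.** Section 9.2 says: "Our sample size of 10 subjects in each group achieves 80% power at a 5% significance level", for a difference of 1.32 SD. Two-sample noncentral t: df = 18, noncentrality = 1.32 × √(10 × 10/20) = 2.95, power 0.797. This agrees with 80%. The attrition table (9.5 points, SD 7) also reproduces: 0.714, 0.771 and 0.819 for N = 16, 18 and 20, against 0.71, 0.77 and 0.82.

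**Power of the planned paired test.** Noncentral t with df = n − 1 and noncentrality = (loss/SD) × √n. At n = 10 and SD 7, half loss gives (4.75/7) × √10 = 2.15, and total loss gives (9.5/7) × √10 = 4.29.

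| n | Half loss (4.75), SD 5 / 7 / 9 | Total loss (9.5), SD 5 / 7 / 9 |
|---|---|---|
| 8 | 0.637 / 0.382 / 0.253 | 0.995 / 0.906 / 0.727 |
| 10 | 0.762 / 0.483 / 0.320 | above 0.999 / 0.967 / 0.843 |
| 12 | 0.849 / 0.573 / 0.386 | 1.000 / 0.989 / 0.914 |

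**Smallest significant loss, n = 10.** The threshold equals the 95% CI half-width, t(0.975, 9) × SD/√10.
- SD 7: 2.262 × 7/√10 = 5.01 points, which is 5.01/9.5 = 53% of the planned gain. A just-significant loss leaves 47%.
- SD 5: 3.58 points (38% lost, 62% left).
- SD 9: 6.44 points (68% lost, 32% left).

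**The two contrasts side by side.** n = 10, SD 7 for each paired difference, true gain 9.5 at Post-treatment 1. Entries are the probability of p < 0.05.

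| True loss by Post-treatment 2 | Planned test (Post 1 vs Post 2) | Baseline vs Post 2 |
|---|---|---|
| 0 | 0.05 | 0.97 |
| 2.5 | 0.17 | 0.80 |
| 4.75 | 0.48 | 0.48 |
| 7 | 0.80 | 0.17 |
| 9.5 | 0.97 | 0.05 |

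**Effect of conditioning on the ANCOVA.** The paired test is run only after a significant primary result, so I checked by simulation whether that selection matters. Settings: 10 per group, true gain 9.5 in Group 1 and 0 in Group 2, normal scores, equal SDs for all pairwise differences, assumed correlation 0.5 or 0.7 between time points, 60,000 trials per setting, keeping trials where the baseline-adjusted ANCOVA favoured Group 1 at p < 0.05. Among those, paired power for SD 5 / 7 / 9 was:
- half loss: 0.765 / 0.511 / 0.379 (correlation 0.5) and 0.765 / 0.519 / 0.389 (0.7);
- total loss: 1.000 / 0.976 / 0.892 and 1.000 / 0.976 / 0.893.

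Conditioning changes little.

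**The case against.** The best defence is that the change whose persistence is in question is the randomised between-group effect, established against a concurrent control. The paired test then asks sensibly whether scores drifted from that level. A before-after change over 24 weeks is exposed to regression to the mean and natural course, and on this reading does not answer the question either. It is also no more precise: with half the gain remaining, its CI excludes zero 48% of the time, the same as the planned test's power for half loss. The 95% CI convention in section 9.4.1 arguably already covers the paired difference, and nothing in the plan says that non-significance will be read as persistence. Durability is not among the aims, objectives or hypotheses, and the half-loss scenario and the SD are assumptions.

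Much of this stands as a limit on the point. The paired contrast is relevant to waning and should be kept. The baseline contrast is uncontrolled and must be labelled so, and the harm depends on how the result is worded. It does not remove the mismatch. No analysis can give a controlled contrast at week 24, because Group 2 is being treated by then. A CI for post-treatment movement still does not estimate what remains from baseline. An exploratory contrast fixed in advance is also worth more than one chosen after the results are seen.

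**Conclusion.** The concern holds. The one analysis named for durability does not answer the question that section 9.4.2 sets for it, and no other section supplies the missing comparison.

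At n = 10 and an assumed SD of 7, half the planned benefit could be lost and the test would still be non-significant about 52% of the time (1 − 0.483; 24% at SD 5, 68% at SD 9). An observed loss of up to 5.0 points would not reach significance. Total loss would usually be detected, so the problem is chiefly partial loss. These figures rest on the assumed SD of the paired difference and on the plan's 9.5-point gain; the mismatch itself does not depend on them.

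Only this conditional follow-on statement is affected. The primary estimate, its Type I error and the sample size are not. It should be corrected because durability is the only follow-on question attached to a positive primary result, and section 2.1 itself cites the need for longer follow-up.

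**What to change.** In section 9.4.2:

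1. Make the Group 1 change in MG-QOL15 from baseline to Post-treatment 2, with its 95% CI, the estimate of whether improvement remains.
2. Keep the Post-treatment 1 to Post-treatment 2 change, with its 95% CI, as the estimate of how much was lost or further gained.
3. State that a non-significant result for the second contrast will not be read as persistence, that a significant loss will not be read as complete loss, and that its direction will be reported.
4. Label both contrasts within-group, uncontrolled and exploratory, because Group 2 is under treatment in that period.

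The cost is a few sentences, one more estimate and a more cautious durability statement. No visits, data or participants are added. The change does not buy precision: at n = 10, with SD 7 (5 to 9) for the baseline to Post-treatment 2 difference, the CI would exclude zero 97% of the time if all 9.5 points remain (above 99% to 84%), but only 48% of the time if half remains (76% to 32%).

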7.1 DISCONTINUATION OF STUDY INTERVENTION/EXPERIMENTAL MANIPULATION

When a participant who signed the consent form chooses to discontinue participation in the study or study intervention, or if the principal investigator and co-investigators determine that a participant should discontinue participation, they will be withdrawn from the study. A withdrawal will either be defined as 'Patient Withdrawal' or 'Principal Investigator Withdrawal'. The participant will be asked to complete an early withdrawal phone call 7-14 days from the date the intervention was discontinued. The purpose of the phone call will be to record any AEs or serious adverse events (SAEs) that may have occurred after the discontinuation of treatment. Research staff will attempt to call the participant up to 3 times.

The data that will be collected at the time of study withdrawal will include the following:

- The reason(s) for discontinuation of the study intervention

The data that will be collected during the early withdrawal phone call will include the following:

- AEs or SAEs that occurred since the time of withdrawal

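### Section 7.1 ends follow-up when a participant stops acupuncture, so the promised intention-to-treat analysis has no planned 12-week score for early stoppers

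*Combined protocol and SAP*

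**What the plan says.** On the analysis set, Section 9.3 states "All analyses will be performed on an intention-to-treat basis", and Section 9.4.2 repeats it for the primary endpoint: "Data will be analyzed per an intent-to-treat approach regardless of actual treatment received". The same section says that the primary change "will be calculated using the first and second collected scores for both groups", and then restricts the analysis: "Only subjects with complete data from both pre-treatment assessment and 12-week assessment will be included in the final analysis".

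On stopping, Section 7.1 covers a participant who "chooses to discontinue participation in the study or study intervention" and one who, in the investigators' judgement, "should discontinue participation, they will be withdrawn from the study". One later contact is planned, the "early withdrawal phone call 7-14 days from the date the intervention was discontinued". Section 7.2 adds reasons for which an investigator may discontinue someone, and Section 8.3.9 requires withdrawal of a participant who becomes pregnant while still being treated.

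On the content of the withdrawal call, Section 7.1 lists only adverse and serious adverse events. Section 1.3, item 8, adds the symptom scale, MG-QOL15 and MG ADL.

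On missing scores, Section 9.4.2 says that if a large proportion is missing, "we will compare baseline characteristics of subjects who completed the treatment with those who were lost to follow-up". It gives no threshold. No imputation and no missing-data sensitivity analysis is planned. The per-protocol analysis in Section 9.3 applies if attendance is poor, and it cannot supply scores that were never collected.

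**The concern.** An intention-to-treat comparison needs the outcome of people who stop treatment. Here the protocol itself ends their data collection, and the complete-data sentence then leaves them out. With about 10 per arm, one or two such losses can move the primary contrast if the reason for stopping is related to outcome. That would favour acupuncture if Group 1 loses poor responders, and count against it if Group 2 loses people who worsen. A baseline comparison cannot detect stopping that is driven by response after baseline.

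There is also an ambiguity that should not be settled after the data are seen in an unblinded trial. If the withdrawal call does collect MG-QOL15, one sentence of Section 9.4.2 could make that off-schedule score the endpoint, while another requires a 12-week assessment.

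**Working it through.** **1. Passages side by side.** Stopping acupuncture leads to withdrawal from the study (7.1), then one call 7-14 days later (7.1), no planned week-12 score, and exclusion under the complete-data sentence (9.4.2). During weeks 0-12 Group 2 has no sessions, so three routes can act only in Group 1: stopping acupuncture, the gap of more than 14 days, and non-compliance with the intervention. The last two are discretionary under 7.2. Leaving the study by choice, loss to follow-up, a confounding treatment and a new exclusion criterion can occur in either arm.

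**2. Timing of the withdrawal call.** A stop on day 28 puts the call on days 28 + 7 = 35 to 28 + 14 = 42, so any score is from weeks 5-6. A call on day 84 needs a stop on days 84 - 14 = 70 to 84 - 7 = 77, that is, weeks 10-11. The call score is therefore not a 12-week score, except by coincidence.

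**3. The plan's own attrition figures (9.2).** Inputs: difference 9.5, SD 7, two-sided 5%, two-sample t-test. The non-centrality is (9.5/7) x sqrt(n1 n2/(n1 + n2)). For 8 v 8 it is 1.357 x 2 = 2.71 on 14 degrees of freedom.
- N = 16: 71.4% (stated 71%)
- N = 18: 77.1% (stated 77%)
- N = 20: 81.9% (stated 82%)

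All three reproduce, with equal loss per arm. If all four losses fell in Group 1 (6 v 10), power would be 68.6%. The power cost of uneven loss is small, so the issue is bias.

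**4. Bias, illustrative only.** The documents give no stopping rate and no link between stopping and outcome. Assumptions: no true effect, 10 v 10, SD of change 7 (from 9.2), baseline-change correlation -0.5, and ANCOVA of change on arm and baseline. The further covariates mentioned in 9.4.2 are not included. Dropout is ranked on a variable that has a set correlation with change, and the worst-ranked are removed. There are 200,000 replicates per setting. Positive bias favours acupuncture.

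| Lost (Group 1 / Group 2) | Correlation | Bias, points | Type I error |
|---|---|---|---|
| 2 / 0 | 0 | 0.01 | 5.0% |
| 2 / 0 | 0.25 | 0.42 | 5.3% |
| 2 / 0 | 0.5 | 0.84 | 6.0% |
| 2 / 0 | 1 | 1.74 | 9.7% |
| 0 / 2 | 0.5 | -0.84 | 6.0% |
| 1 / 0 | 0.5 | 0.45 | 5.4% |
| 2 / 2 | 0.5 | 0.00 | 5.4% |
| 3 / 1 | 0.5 | 0.78 | 6.1% |

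Check: the unadjusted t-test gives 1.11 points for 2 / 0 at 0.5. Baseline adjustment should scale this by 1 minus the squared baseline-change correlation: 1.11 x (1 - 0.25) = 0.83, which agrees with 0.84. With a baseline-change correlation of 0, -0.3 or -0.7, the simulated bias is 1.11, 1.02 or 0.58.

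**5. Scale.** The standard deviation of the estimate with 8 v 10 is about 7 x sqrt(1 - 0.25) x sqrt(1/8 + 1/10) = 2.88, or roughly 3 once the baseline slope is also estimated. Then 0.84/3 = 0.28 of that standard deviation, and 0.84/9.5 = 9% of the planned difference. At correlation 1 the bias is 1.74/9.5 = 18% of it.

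**The case against.** The strongest reply is that the two sentences of Section 9.4.2 are compatible: analyse the available pairs by randomised arm, whatever treatment was received. That stands. A reader might infer that the complete-data sentence alone breaks intention-to-treat, but the gap is created by the end of follow-up in Section 7.1, and the remedy below keeps the planned ANCOVA.

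Second, Section 1.3, item 8, does plan an MG-QOL15 at the withdrawal call, so on one reading an early stopper has a second score and stays in. This also stands as a reading. It means that exclusion is not certain, but the score used would usually be off schedule.

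Third, it is close to a truism that untreated people cannot stop treatment. A reader might infer from the asymmetry that Group 1 will lose more people, or that the result will lean towards acupuncture. The documents support neither: they give no stopping rate, Group 2 can leave during an unblinded wait, and loss from Group 2 produces the mirror-image bias.

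Fourth, the plan does address attrition: power under 20% loss (9.2), at least five contact attempts (7.3), and payments tied to completed surveys (5.5). These may reduce loss or describe its cost in power. None measures or bounds bias.

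Fifth, interviewing stoppers at week 12 might mix time points within Group 1. Twenty-four sessions have 23 gaps. At 3.5 days each they take 80.5 days, and one permitted 14-day gap makes it 22 x 3.5 + 14 = 91 days. That spread is already in the plan, and week 12 matches both Group 2's assessment and the 12-week assessment that Section 9.4.2 names.

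**Conclusion.** The point holds as a cheap improvement of moderate to low severity. The plan promises an analysis regardless of treatment received, but it arranges no 12-week score for those who stop acupuncture, and it is inconsistent about what the withdrawal call collects. At a moderate dropout-outcome correlation, two losses from one arm give a bias of about 0.8 points, roughly 0.3 of the estimate's standard deviation, and a type I error of about 6%. The 1.7 points and near-10% error require dropout to be ranked perfectly on outcome, so they are an extreme case and not an expectation. The number lost, the dropout-outcome correlation and the baseline-change correlation are all assumed; only the SD of 7 and the group size of 10 come from Section 9.2. The documents do not determine the direction or the size of the actual bias.

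**What to change.** (a) Leave every treatment-stopping rule unchanged, but separate stopping acupuncture from ending data collection. Ask early stoppers, under one rule for both arms, for the existing phone MG-QOL15 and MG ADL interview at 12 weeks after baseline, unless they withdraw consent or the best-interest reason in Section 7.2 applies. Reconcile this with Section 7.1, Section 7.2 reason 5 and Section 8.3.9, which require or allow withdrawal from the study, so that the text says consistently whether outcome data are still collected in those cases. The scheduled visit for participants still on treatment does not move.

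(b) Reconcile Section 7.1 with Section 1.3, item 8, on what the withdrawal call collects, and state in Section 9.4.2 that a withdrawal-call score is not the 12-week score.

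(c) Keep the planned ANCOVA on all available 12-week scores as randomised. Report missing scores by arm and reason. Add a delta-shift or tipping-point sensitivity analysis by arm, with its range fixed before analysis. As a scale, a 7-point shift for 2 of 10 participants moves that arm's mean by 7 x 2/10 = 1.4 points.

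Cost: a protocol amendment, one call of about 20 minutes (the protocol's own duration) per early stopper, and an estimate that may be diluted by people who stopped, which is what intention-to-treat estimates. Scores for anyone already withdrawn cannot be recovered.
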